5.2 Exclusion Criteria

- Pregnancy or breast feeding
- Active drug use or alcohol abuse/dependence, which in the opinion of the investigators will interfere with the patient's ability to participate in the study
- Serious illness requiring systemic treatment and/or hospitalization within 30 days of entry
- Evidence of active opportunistic infections or neoplasms that require chemotherapy during the study period except cutaneous Kaposi Sarcoma
- Allergy or hypersensitivity to atorvastatin or any of its components
- History of myositis or rhabdomyolysis with use of any statins
- History of inflammatory muscle disease such as poly or dermatomyositis
- Concomitant use of fibric acid derivatives or other lipid lowering agents including patients on statins and Ezetimibe
- Concomitant use of drugs that have significant interactions with atorvastatin. Please see appendix II for a listing,
- Concomitant use of St.Johns wort
- Concomitant use of Valproic acid

- Patients who are on concurrent immunomodulatory agents, including systemic corticosteroids will be ineligible for 3 months after completion of therapy with the immunomodulating agents. Topical, nasal or inhaled corticosteroids use is not an exclusion criteria
- Serum LDL cholesterol less than 40 mg/dl
- Vaccinations within 6 weeks of study entry.

5.3 Study enrollment procedure overview

Prior to implementation of this protocol, sites must have the protocol and informed consent forms approved by their local institutional review board (IRB). Health care providers at participating institutions will identify eligible patients. At the National Naval Medical Centers all providers and research nurses at the Infectious Disease Clinic (IDSI) will identify eligible patients. Once a candidate for study entry is identified, patients will be approached by their providers or research nurses about the protocol. If the candidate is interested details of the protocol will be reviewed with the candidate by the study PI/designee. If the volunteer is willing to participate in the study, they will be provided with copies of the informed consent to review. After all questions, about the study and the informed consent, have been answered to the participant's satisfaction, they will be asked to sign the IRB approved consent form.

Volunteers enrolled at the NIH will be required to sign a screening consent to undergo screening laboratories for the study. Patients who satisfy inclusion criteria and are willing to participate in the study will be required to sign the study informed consent. Since study participants at NNMC receive their routine care at NNMC screening consents will not be used at the NNMC prior to study enrollment. Volunteers at NNMC will be required to sign the study consent only.

It is anticipated that most subjects will have their routine immunizations prior to signing informed consent. However, in the event routine vaccination is required after the subject has been randomized; for DOD sites (NNMC and NMCSO) we will attempt to vaccinate the individual after completion of the week 8 visit or at the end of the study phase of the protocol. For subjects vaccinated during the wash-out phase or at the end of the study the wash-out phase

or the last study visit will be extended by 2 weeks. For patients seen at the NIH site, the protocol will not administer routine vaccinations, with the exception of the influenza vaccination. It is anticipated for some patients, participation may overlap with influenza season and that influenza vaccination will be necessary in the event that protocol participation begins prior to but extends into, influenza season. For such patients, standard, inactivated influenza vaccination will be administered (if necessary) during the week 8 visit. For subjects vaccinated during the wash-out phase or at the end of the study the wash-out phase or the last study visit will be extended by 2 weeks. Extension of both these study phases is necessary because of the effects of vaccination on viral kinetics.[33]

Definitions for Schedule of Events – Timing of Evaluations

5.3.1 Prerandomization evaluations

After signing either the screening/study informed consent, patients will undergo screening tests. Screening will include a complete medical history and physical examination. Laboratory testing will include a fasting lipid profile, flow studies (FACS), routine safety labs which will include a liver function test and creatinine kinase assay, a hepatitis profile and viral load assay to establish baseline viral load. Due to the variability in the viral load assay, we will utilize a minimum of 3 viral load assays to establish a baseline. All testing will need to be completed within a 4 week period prior to randomization. During this period, patients may come in for testing at their own convenience, but testing will not be done more than once within a 24 hour period. All laboratory tests except standard safety labs will be done centrally at SAIC Frederick to maintain consistency. Volunteers at the NIH who satisfy the inclusion criteria and who continue to be interested in the protocol will be now required to sign the study consent.

5.3.2 Randomization scheme

Subjects will be randomized after the investigators have ascertained that the subject meets criteria for inclusion. Prior to randomization investigators will ensure that the patient understands the risks and benefits associated with the study and informed consent has been signed. Randomization will be done using a random number table generated by the NIH pharmacy department. 11 patients will be randomized to the placebo arm of the study and 11 to the drug arm of the study initially. The 11 patients randomized to placebo will then cross over after completion of 12 weeks on study (8 weeks on study treatment and 4 weeks wash out) to the

study arm and vice versa patients in the atorvastatin arm will cross over the placebo arm after 12 weeks on study

5.3.3 Study entry

On the day patients get randomized, patients will undergo routine safety labs including liver function tests (LFT), creatinine phosphokinase, hematological parameters, fasting lipids including apolipoprotein B, hsCRP, plasma HIV viral load and a full FACS. Patients will also have a sample of blood stored for future phenotyping and genotyping. Patients will be required to answer both the Piper Fatigue Scale and the Beck Depression Inventory.

5.3.4 On study evaluations

Efficacy Assessments

Patients will undergo HIV BDNA assays on days 7, 14, 42, 56, 84, 91, 98, 126, 140 and 168. Patients will also undergo evaluation for immune activation markers levels specifically CD38 and HLA-DR expression on CD4 and CD8 cells and Ki67 will be done on days 7, 56, 84, 91, 140 and 168. Fasting lipids, apolipoprotein and ultrasensitive hsCRP will be done at randomization and on day 7, 56, 84, 91, 140 and 168. All testing other than standard safety testing will be done at SAIC Frederick. The Beck depression inventory and the Piper fatigue scale will be administered on days 56, 84, 140 and 168.

Safety assessments

Safety assessments will be done at specified study visits and will include clinical assessment, physical exam, medication assessment, routine chemistry and hematology, serum creatinine phosphokinase, liver function tests, and serum pregnancy tests. The Piper Fatigue Scale will be administered prior to and following each arm. Please see table 1 for details. All safety labs will be done at the individual institutions. All laboratories performing study related tests are CLIA certified laboratories

Genetic studies

TSG 101 genotyping and HLA typing will be performed. Additional genotyping of specific host genes will be performed as indicated. Additional blood will be obtained as indicated for storage and future use.

Adherence assessment

Pill counts will be performed at each visit to monitor adherence to the protocol, and patients will be asked about adherence.

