3.2 Secondary objectives

- To compare the changes in the expression of immune activation markers between the placebo phase and the atorvastatin phase.
- To investigate HIV-1 and TSG 101 phenotypes among enrollees
- To investigate the changes in the metabolic profile between the placebo and the atorvastatin phase
- To investigate the safety profile of atorvastatin in HIV positive patients not on antiretroviral therapy
- To compare the subjective and objective evaluation of fatigue during the atorvastatin and placebo phase

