4.0 STUDY DESIGN

Study design

This study utilizes a case cross over design to investigate the effects of atorvastatin on HIV viral load, immune activation markers and metabolic profile. Figure 2 is a diagrammatic representation of the study design. A double blind strategy was chosen for the design of this trial. In general statin therapy is associated with a number of side effects, some of which, including

fatigue and muscle aches may be highly subjective or multifactorial in origin. If statins do show an antiviral effect, then their use will be balanced by well described adverse effects. We wish to evaluate such adverse effects in detail in patients enrolled in the trial, and feel double blind approach is the most rigorous and objective.

HIV positive patients, who have been off anti-retroviral medications for a minimum of 3 months and with no documented evidence of resistance, will be recruited for this study. Each subject will have 3 baseline viral loads and will be randomized to receive either 80 mg of atorvastatin or placebo for 8 weeks. Following this, there will be a 4 week wash out phase. Upon completion of the wash out phase patients who were initially on the atorvastatin arm will switch to the placebo arm, while patients who started in the placebo arm will switch to atorvastatin to complete an additional 8 weeks. All patients will be followed for 4 more weeks upon completion of study medications. The study design is schematically represented in Figure 2.

[figure not shown]

Figure 2 - Graphical representation of the study design (time represented in weeks)

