5.3.5 Post treatment evaluations

4 weeks after treatment discontinuation (\pm 1 week), patients will have repeat viral load, lymphocyte sub set analysis, immune activation parameters, safety labs including LFTs and creatinine phosphokinase. All visits will be completed on the indicated days of the protocol, for unforeseeable circumstances that might render the patient unable to complete the study visit on the designated days the patient may reschedule within a 2-5 day window except for the end of study visit which may be completed within a 1 week window.

5.4 Subjects can be discontinued from the study for the following reasons:

- Failure to comply with the protocol
- If they develop a serious adverse event (SAE)
- Pregnancy, if a patient becomes pregnant on study; she will stop the study drug and be followed as part of the study through the pregnancy including the peri-partum period to ensure her safety.
- **Any subject with a creatinine phosphokinase (CPK) value greater than 10 times the upper limit of normal (i.e grade 3 or higher), will undergo repeat testing. Repeat testing will be conducted at protocol specified time points (i.e. within 1-3 days of the initial result and also at day 7). Persistently elevated laboratory values, i.e. CPK measurements that remain at the same level or are higher than the initial value, on three consecutive determinations, despite cessation of exercise will result in study drug discontinuation.**
- **In addition, all CPK elevations associated with grade 3 or higher symptoms or for significant symptoms or elevations in CPK that do not fall into either of the above mentioned categories; a conference call with representatives from all three participating sites (either the PI or their designee) will be initiated. Decisions regarding study drug discontinuation for patients meeting the above listed criteria will be made on an individual case by case basis. The medical monitor at the sites will be involved in all decisions regarding study drug discontinuation.**

- Patient develops liver function elevations 3 times the upper limit of normal
- If the serum LDL cholesterol falls to less than 40mg/dl
- Develops a grade 2 or greater allergic reaction to the medicine or develops signs and symptoms of an immediate hypersensitivity reaction to the medication
- Patient needs to start antiretroviral agents using current DHHS guidelines as recommendations.

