- Patient develops any condition that the study investigators deem would be detrimental for the patient to continue on the study
- If the patient desires to leave the study
- Patient starts taking other lipid lowering drugs including fibric acid derivatives, bile acid sequestrants and niacin preparations
- Patients will be dropped from the study if their CD4 count drops by fifty percent on two successive determinations, or falls below 250 cells/ μ l in the absence of any documented ongoing infections/inflammatory processes while on study

If subjects are discontinued from the study secondary to any of the above given reasons they will be replaced according to the prior randomization.

CLINICAL AND LABORATORY EVALUATION

Evaluation*	Screening	Randomization	D7 W1	D14 W2	D42 W6	D56 W8	D84† W12	D91 W13	D98 W14	D126 W18	D140 † W20	D168 W24
Documentation of HIV	Pos ELISA and Confirmatory Blot, previous results will be allowed											
Medical /Medication history	✓	✓	✓	✓	✓	✓	✓	✓	✓	✓	✓	✓
Nadir CD4	✓											
Clinical Assessment	✓	✓	✓	✓	✓	✓	✓	✓	✓	✓	✓	✓
Questionnaires		✓				✓	✓				✓	✓
Physical Exam	✓	✓				✓	✓				✓	✓
Hepatitis profile	✓											
Fasting lipid profile	✓	✓	✓			✓	✓	✓			✓	✓
Markers of inflammation		✓	✓			✓	✓	✓			✓	✓
Hematology	✓	✓		✓	✓	✓	✓		✓	✓	✓	✓
Chemistry including CK	✓	✓		✓	✓	✓	✓		✓	✓	✓	✓
Liver Function Tests	✓	✓		✓	✓	✓	✓		✓	✓	✓	✓
Urinalysis	✓	✓				✓	✓				✓	
Pregnancy Testing	✓	✓	✓	✓	✓	✓	✓	✓	✓	✓	✓	✓
Full FACs	✓	✓	✓			✓	✓	✓			✓	✓
HIV viral load (bdna)	✓ (3 viral load measures will be used to establish baseline)	✓	✓	✓	✓	✓	✓	✓	✓	✓	✓	✓
Statin/placebo		✓	✓	✓	✓	✓	✓	✓	✓	✓	✓	
Stored Plasma/PBMC		✓	✓	✓	✓	✓	✓	✓	✓	✓	✓	✓
Stored Sera		✓				✓	✓				✓	

- * Study consent will be signed at NNMC prior to screening and at randomization at the NIH
- † In the event subject is vaccinated these visits will be extended by 2 weeks

Table 1- Schedule of events

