Myalgia and rhabdomyolysis have been reported with atorvastatin use. In the ASCOT study there was a single case of non-fatal rhabdomyolysis among 5168 patients randomized to atorvastatin. [40] In a study of secondary prevention of CAD, among 10,000 patients randomized to receive either 10 or 80 mg of atorvastatin there were 5 cases of rhabdomyolysis.[39] While rhabdomyolysis is a complication of atorvastatin it appears relatively rare.

The risk of myopathy is increased when atorvastatin is used in conjunction with azole antifungals, erythromycin, clarithromycin, niacin, fibric acid derivatives or cyclosporine [37]. Patients who use fibric acid derivatives, niacin and cyclosporine will not be enrolled into the

study. Patients who start azoles or erythromycin or clarithromycin while on study will be monitored closely for signs and symptoms of myopathy, patients on these drugs at the time of enrollment will not be eligible for this study until completion of therapy with these agents.

In addition the risk of myopathy is increased with the concomitant use of grape fruit juice and atorvastatin. These interactions are mediated via the cytochrome p 450 system; grape fruit juice is an inhibitor of this system [41] While on study patient will be advised to avoid grape fruit juice and grape fruit.

To reduce risk to our study patients we will monitor liver function (LFT) and creatinine phosphokinase (CPK) at baseline and as indicated in the schedule of events. Patients will also be questioned about myalgia or weakness at each visit. Presence of any of these symptoms will require complete evaluation as judged suitable by their health care provider. Patients who participate in this study will be asked to refrain from vigorous exercise regimens for the study period. Vigorous exercise is known to increase CPK levels and may cause patients to be unnecessarily excluded /withdrawn from the study.

- Pregnancy and breast feeding are contraindications for atorvastatin use; atorvastatin is classified as a pregnancy category X drug. Pregnant or nursing women will not be enrolled in this study and patients will be required to use reliable methods of contraception to be enrolled in this study. If a patient becomes pregnant on study, she will be asked to stop taking study drug and will be followed through her pregnancy and the peripartum period.

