Secondary Objectives for Statistical Consideration

1- To study the difference in the expression of immune activation markers (i.e HLA DR CD38 and Ki67 expression both percentage and number on CD4+ and CD8+ cells) between the end of 7 weeks and the end of 19 weeks in the placebo and atorvastatin sequence. All comparisons of changes between the end of 7 weeks and the end of 19 weeks, i.e. the difference between months 19 and 7 or months 7 and 19 will be conducted by using the paired t-test if the measurements are continuous. McNemar statistic will be used for the changes of discrete markers.

Because of the randomization, the baseline measurements (at beginning of this trial) in placebo and atorvastatin sequences should have the same distribution. This information can be incorporated into an additional statistical analysis, called analysis of covariance ANCOVA. A linear mixed effects model can be used to analyze the difference between the change of viral loads evaluated at the beginning of this trial and at the end of the 7th week, and at the end of 11th week and 19th week in atorvastatin and placebo sequence and placebo and atorvastatin sequence. The difference of viral load at the end of 11th week in two treatment sequences can be used to assess whether there is a treatment carryover effect.

Additional analyses will be conducted to assess whether there is any effect of drug on change viral load, beyond that predicted by the change in LDL.

Finally the correlation between reductions in serum cholesterol and HIV viral load in treatment arm will be assessed by using Spearman's correlation coefficient statistics.

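### On-drug fatigue is scored only on the last day of each phase and early stoppers are replaced, so the atorvastatin–placebo fatigue comparison covers only patients who stayed on drug to the end of the phase

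*Combined protocol and SAP*

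**What the plan says.** Section 3.2 lists as its last secondary objective "To compare the subjective and objective evaluation of fatigue during the atorvastatin and placebo phase". Section 4.0 names fatigue and muscle aches among the subjective effects of statins, adds "We wish to evaluate such adverse effects in detail in patients enrolled in the trial", and gives this as the reason for the double blind.

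The Piper Fatigue Scale is completed on the day of randomization (Section 5.3.3). After that, Section 5.3.4 states "The Beck depression inventory and the Piper fatigue scale will be administered on days 56, 84, 140 and 168". Its safety paragraph adds "The Piper Fatigue Scale will be administered prior to and following each arm" and refers the reader to Table 1, where the questionnaires row shows the same fixed days and no early-termination visit.

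Section 5.4 lists the grounds for discontinuation. They include a serious adverse event, persistent CPK elevation, liver tests at three times the upper limit, LDL below 40 mg/dl, a need for antiretrovirals, and the patient's own wish. Of patients discontinued on any of these grounds it says "they will be replaced according to the prior randomization".

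Section 7.0 describes no fatigue analysis, no analysis set and no handling of early stoppers. The nearest rule is the one for activation markers: "All comparisons of changes between the end of 7 weeks and the end of 19 weeks", by paired t-test when the measurement is continuous.

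**The concern.** A patient who stops study drug before the last day of a phase has no on-drug fatigue score for that phase, and a replacement patient takes the place. The scores that remain are those of patients who stayed. If early stopping on atorvastatin is related to fatigue, the most affected patients are missing from the comparison meant to detect it, and a null result could be read as reassurance about a side effect the protocol singles out. The gap lies in data collection: a score that was never taken cannot be recovered at analysis.

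**Working it through.** **The plan's own figure.** The plan gives no power or precision figure for fatigue. Its viral load power does reproduce. The SD of the paired difference is 0.74 × √(2 × (1 − 0.75)) = 0.523. A two-sided paired t-test at 0.05 with 20 patients then has power 77.1%, 90.0% and 98.2% for differences of 1/3, 0.4 and 0.5 log10, against the stated 77%, 90% and 98%. That calculation does not bear on this point.

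**Which fatigue scores are on drug.** Treatment runs from day 0 to day 56 and from day 84 to day 140 (Sections 4.0 and 5.3.4, Table 1).

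| Piper day | Position |
|---|---|
| 0 | before phase 1 drug |
| 56 | last day of phase 1, on drug |
| 84 | end of washout, before phase 2 drug |
| 140 | last day of phase 2, on drug |
| 168 | four weeks after drug |

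**On-drug measurements per phase in Table 1.**

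| Measurement | Phase 1 days | Phase 2 days | Number per phase |
|---|---|---|---|
| Questionnaires | 56 | 140 | 1 |
| Liver tests and CK | 14, 42, 56 | 98, 126, 140 | 3 |
| Viral load | 7, 14, 42, 56 | 91, 98, 126, 140 | 4 |

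A stop on any of days 1 to 55 of a phase leaves no scheduled on-drug score. If the paired rule in Section 7.0 were applied to fatigue, it would need both day 56 and day 140, so such a patient would drop out of the comparison altogether.

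**Size.** Let 22 patients complete, because stoppers are replaced. Let k further patients stop atorvastatin early. Let their fatigue rise exceed the completers' by e, in SDs of the within-patient difference. If the completers' mean is m, then

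- mean over all takers = [22m + k(m + e)] / (22 + k) = m + ek/(22 + k)
- understatement by the completers' mean = ek/(22 + k)

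| k | e = 1 | e = 2 |
|---|---|---|
| 0 | 0 | 0 |
| 1 | 1/23 = 0.04 | 2/23 = 0.09 |
| 2 | 2/24 = 0.08 | 4/24 = 0.17 |

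The documents give neither k nor e. The only scale for k is the 10% loss to follow-up in Section 7.0: 0.10 × 22 = 2.2, about two patients over both treatments and all causes. So k = 2 puts that entire loss on atorvastatin for symptoms, and k = 1 is an even split between treatments.

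**The case against.** Several points on the other side stand.

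- **Symptoms are captured by other routes.** Adverse events are graded and judged for causality under the blind, clinical assessment takes place at every visit, and Section 6.1 says "Patients will also be questioned about myalgia or weakness at each visit". Fatigue in an early stopper would still be recorded. These records are not the Piper scale, however, and no comparison of them between treatments is planned.
- **Leaving is not the same as failing to tolerate.** A reader might infer that only patients who tolerated treatment are compared. The documents do not support that. Fatigued patients who stay are scored, and many exits in Section 5.4 (low LDL, starting antiretrovirals, CD4 decline, non-compliance, pregnancy) need not involve symptoms. Fatigue is not itself a listed criterion. It would act through a serious adverse event, investigator judgement, the case-by-case CPK and symptom call, or the patient's wish.
- **The scale might be given at an early stop.** The wording in Section 5.3.4 could cover an arm that ends early. The post-treatment list in Section 5.3.5, which runs to "safety labs including LFTs and creatinine phosphokinase", names no questionnaire, but that is weak evidence: Table 1 schedules one at the day 168 post-treatment visit all the same. What remains is that no early-stop score is explicitly required and that Table 1, to which the sentence refers, shows fixed days only.
- **Few early stops are likely.** The protocol's figures for persistent liver enzyme rises at 80 mg are 1.2% (Section 6.1) and 2.3% (Section 9.2.1), or 0.3 to 0.5 of 22 patients. Rhabdomyolysis is rarer still. Stops on placebo by fatigued patients would partly offset the bias.

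A reader might also infer a severe loss of power. Large losses appear only with about four atorvastatin stoppers, roughly double the plan's total expected loss. Adding stoppers 2 SD more fatigued also widens the spread among all takers, so a drop measured from a fixed 80% reference overstates the loss in that case.

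**Conclusion.** The point holds, with narrow scope and minor priority. The schedule gives one on-drug fatigue score per phase, on its last day, requires none at early stopping, and replaces those who stop. The scale comparison therefore describes patients who stayed on drug to the end of the phase.

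The direction is conditional: fatigue on atorvastatin is understated if those who stop it early are more fatigued than those who finish. No direction is claimed for stops unrelated to symptoms. At the planned loss, the understatement is at most about 0.17 SD, and that requires both lost patients to have stopped atorvastatin for symptoms with a 2 SD excess. With one such patient it is 0.04 to 0.09 SD. If nobody stops early, or stoppers are no more fatigued than completers, it is zero.

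It would be wrong to infer that adverse event monitoring is deficient, or that this gap in the fatigue scores undermines the viral load result or the sample size.

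**What to change.** 1. Give the Piper scale on days 42 and 126, at visits already held, and at the visit where drug is stopped early, before any unblinding under Section 5.5. The day 42 and 126 forms do not help patients who stop sooner; the stop-visit form does.
2. In Section 7.0, compare on-drug fatigue scores in everyone dosed, including patients later replaced. Use a mixed model with treatment, period, visit, pre-phase score and a random patient effect. Keep the paired end-of-phase test as supporting.
3. Report the number of early stops and the reasons for them, by treatment.

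The cost is 2 × 22 = 44 more Piper forms, one more per early stopper, and a paragraph of analysis text. No scheduled visit or blood draw is added.

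The downside is that a score taken at stopping may be raised by the decision to stop or by knowledge of a laboratory result. Record the days since last dose, and show the result with and without stop-visit scores. A patient who leaves during the first phase will still have no second-phase score, so the fix lessens the gap without removing it.
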